- LMCA stroke as indicated by the presence of aphasia and MRI lesion in the LMCA distribution
- Moderate aphasia (Token Test score between 40th and 90th percentile)
- Fluency in English
- Provision of written informed consent by the patient and/or the next of kin

The exclusion criteria include:

- Age less than 19 years
- Underlying degenerative or metabolic disorder or supervening medical illness
- Severe depression or other psychiatric disorder
- Positive pregnancy test in women of childbearing age
- Any contraindication to MRI/fMRI at 3T (i.e., intracranial metal implants, claustrophobia)
- Any contraindication to nerTMS (e.g., seizures or epilepsy)

Screening will also include a complete medical history, details of the precipitating event, physical examinations, complete baseline and ongoing vital sign assessments, neurological evaluations, laboratory results and diagnostic imaging performed. Screening assessments will be performed by the clinician involved in the care of the patient to determine subject eligibility criteria especially neurological examination, which will be documented as part of the patients' medical record.

For the randomized controlled trial (RTC; Figure 1), once informed consent and HIPAA authorization for research are obtained, the subject will be randomized. Randomization will be conducted by the study biostatistician and will be implemented using a standard sealed envelope process.

For the un-blinded observational study (OBS; Figure 2), once informed consent and HIPAA authorization for research are obtained, the subject will be scheduled for group therapy with CIAT where rTMS will be used as a primer for improved rehabilitation outcomes. Three to four subjects will be scheduled concurrently in order to achieve the required minimum of 3 subjects per CIAT therapy group. These subjects will not be randomized or blinded to the treatment.

A member of the research study staff will monitor the subjects for continued compliance with Inclusion and Exclusion Criteria. Those subjects who do not meet the continuation criteria will be terminated from the study.

DAY 2 (pre-nerTMS; days 1 and 2 may be combined)
All subjects (RTC or OBS) will undergo the same procedure

Data Collected for Study Enrollment (after signed consent):

Upon Admission:

Demographics

Medical history (including any chronic underlying disease and medications)

Contact information to include phone number

Time, date, and mechanism of stroke

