All these individuals already expressed their interest in participating in the Data Safety Monitoring Board for this study. Drs. [name] and [name] will be responsible for providing updated efficacy and tolerability data to the DSMB every six months (at least 2 weeks prior to the DSMB meeting). The DSMB will assess the risks and benefits of study participation to all subjects and based on this assessment the DSMB will provide a written report of their analyses and recommendation as to whether the study should continue, whether modification to the study are needed or if the study should be terminated. [name], in conjunction with the DSMB, will be responsible for making certain that the DSMB files their report to the IRBs and NINDS. The DSMB will also provide the investigator with a summary of their report that will include their recommendations.

Adverse events will be monitored during the study using clinical interviews and examinations that will be administered by a board certified neurologist ([name]) who has had more than 10 years experience conducting clinical investigations of stroke in adults. [name] (or in his absence another experienced neurologist) will be responsible for evaluating all adverse events during study visits, which will occur at the beginning and the completion of the study or more frequently as necessary. Further, the rTMS Team will supervise all nerTMS sessions and report any adverse events to the PI. Additionally, a study related physician (typically, [name]) is accessible by pager to patients, their legal guardians, hospital and research staff 24 hours/day, 7 days/week. Drs. [name] will be responsible for monitoring all baseline and post-baseline assessments.

An adverse event (AE) is any unexpected medical occurrence in a patient or clinical investigation subject who is administered a treatment (nerTMS and/or CIAT) and which does not necessarily have a causal relationship with the treatment. This includes any clinical change that occurs at any time following consent that does not typically occur in that subject and is considered clinically significant. The frequency and severity of all observed or volunteered AEs regardless of treatment group or suspected causal relationship to the study treatment will be recorded throughout the study. [name], with oversight from the DSMB, will be responsible for determining causal relationship between the study treatment and all AEs.

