Withdrawal from the study as a result of an AE or because of therapeutic measures taken to treat an AE will be at the discretion of [name]. If a subject withdraws or is withdrawn from the study for any reason, [name] will monitor subjects with any

ongoing AE until the AE is resolved or determined to be stable. All AEs (including those present during screening) will be reported. However, for analytics purposes, only post-baseline (randomization) AEs will be considered for calculating treatment group differences in AEs.

A serious adverse event (SAE) is any adverse experience occurring at during study participation that results in any of the following outcomes: death; a life threatening adverse drug experience; inpatient hospitalization or prolongation of existing hospitalization; a persistent or significant disability/incapacity. Important medical events that may not result in death, be life-threatening, or require hospitalization may be considered serious adverse experiences when, based on appropriate medical judgment of the study physician, they may jeopardize the patient and may require medical or surgical intervention to prevent one of the outcomes in this definition. The judgment of whether a particular AE meets the above criteria for an SAE for the proposed study will be determined by [name], in conjunction with the proposed DSMB. It will also be [name] responsibility to manage all SAEs and to make referrals for appropriate care, as necessary. All SAEs will be reported to the University of Alabama at Birmingham Institutional Review Board, the study DSMB, and the NINDS project officer within 72 hours of their discovery. The study blind may be broken at any point throughout the study as needed to protect the safety of a subject. All subject information will be de-identified when reporting SAEs. All AEs and SAEs will be entered into a database that is de-identified and password protected to ensure confidentiality. [name], in collaboration with [name], will ensure that all patients have appropriate follow-up care after their study participation.

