The Charter will define the primary responsibilities of the DSMB, its membership, and the purpose and timing of its meetings. The Charter will also provide the procedures for ensuring confidentiality and proper communication, the statistical monitoring guidelines to be implemented by the DSMB, and an outline of the content of the Open and Closed Reports that will be provided to the DSMB.

2. Primary Responsibilities of the DSMB

The DSMB will be responsible for safeguarding the interests of trial participants, and assessing the safety and efficacy of the interventions during the trial (rTMS and or combined rTMS and CIAT). This responsibility will be exercised by providing recommendations about stopping or continuing the trial. To contribute to enhancing the integrity of the trial, the DSMB may also formulate recommendations relating to the selection/recruitment/retention of participants, their management, improving adherence to protocol-specified regimens and retention of participants, and the procedures for data management and quality control.

The DSMB will be advisory to the principal sponsor-investigator [name], PhD. The PI will be responsible for promptly reviewing the DSMB recommendations, to decide whether to continue or terminate the trial, and to determine whether amendments to the protocol or changes in study conduct are required. *If an investigator does not agree with the DSMB recommendations then a memo justifying the reasons for not complying with the recommendations must accompany the minutes.*

3. Membership - a. Members

The DSMB will consist of at least 4 independent clinicians and biostatisticians that, collectively, have experience in the management of patients with strokes associated with aphasia and in the conduct and monitoring of randomized clinical trials. A quorum will require at least 3 members, including the chair.

DSMB Chair: [name]
CAHS Rehabilitation Sciences
[contact]
[name]

Biostatistician: [name]
Department of Public Health
[contact]
[name]

Other DSMB Members:

[name]
Department of Neurology
[contact]
[name]

[name]
Department of Neurology
[contact]
[name]

Conflicts of Interest

The DSMB membership has been restricted to individuals free of apparent significant conflicts of interest. The source of these conflicts may be financial, scientific or regulatory in nature. Thus, study investigators are not members of the DSMB.

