The DSMB members will disclose conflicts of interest to fellow members. Any DSMB member who has or develops a significant conflict of interest should resign from the DSMB.

DSMB membership is for the duration of the clinical trial. If any members leave the DSMB during the course of the trial, the PI will promptly appoint their replacement.

4. Timing and Purpose of the DSMB Meetings

The first meeting of the DSMB will occur 3 months after study initiation (official date of the IRB approval). The reviews will be done in person or via teleconference. The study team is responsible for coordinating the venue for the DSMB meetings, i.e. establishing the meeting date and time, reserving the conference room, arranging for teleconference equipment. The purpose of the DSMB meetings is to review the conduct of the trial to date and assess safety and efficacy of the study intervention (rTMS). The DSMB will review SAEs and determine whether the study should be prematurely discontinued.

Ad hoc meetings may be scheduled as needed.

5. Confidentiality

A format for Open and Closed Sessions should be implemented. The intent of this format is to enable the DSMB to preserve confidentiality of the comparative efficacy results while at the same time providing opportunities for interaction between the DSMB and study team. DSMB personnel will not have access to unblinded data; group comparisons will be provided by study statistician ([name]).

The study arm assignment for individual participants may be disclosed on a case-by-case basis. Request to unblind must be provided by DSMB Chair in writing. The DSMB will have responsibility for assessing and making recommendations to correct any possible abuses of the disclosure privilege.

6. Communication

Open Session

The Open Session provides the DSMB an opportunity to query the study team about issues that have arisen during the review of the data.

Closed Session

Sessions involving only DSMB membership and the independent biostatistician who generated the Closed Reports will be held to allow discussion of confidential data from the clinical trial, including information about the relative efficacy and safety of interventions. The DSMB will develop a consensus on its list of recommendations, including whether the trial should continue.

DSMB Meeting Minutes

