Depending on the issues and protocol, a DSMB meeting may have both Open and Closed meeting minutes. Meeting minutes should be distributed as soon as possible after the DSMB meeting. IRB needs to be included on the distribution list. At the time of IRB annual renewal, DSMB minutes will be required, if not already provided.

7. Statistical Monitoring Guidelines

Study will not be terminated if there is evidence that one of the treatment conditions has better side effects profile or efficacy unless statistically significant difference in favor of one of the treatment arms is observed in at least 50% of the variables.

8. Content of Reports for the DSMB

- Study number and title. Brief summary of the study design.
- Protocol amendments
- Status of accrual. If accrual is slower than expected, a plan for increasing enrollment.
- Status of participating sites (for Multi-Center trials)
- Compliance

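### The DSMB manual's 50%-of-variables condition for stopping covers side effects as well as efficacy, and nothing says it yields to the board's safety role

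*Combined protocol and SAP*

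**What the plan says.** Section 7 of the DSMB manual (Statistical Monitoring Guidelines) is a single sentence: "Study will not be terminated if there is evidence that one of the treatment conditions has better side effects profile or efficacy unless" a "statistically significant difference in favor of one of the treatment arms is observed in at least 50% of the variables". It does not list the variables, and gives no significance level or test. Section 1 of the manual describes these as "the statistical monitoring guidelines to be implemented by the DSMB".

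Three other provisions deal with stopping and carry no significance condition:

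- Manual, section 2: "The DSMB will be responsible for safeguarding the interests of trial participants". The board does this through recommendations to stop or continue.
- Manual, section 4: "The DSMB will review SAEs and determine whether the study should be prematurely discontinued".
- Data Safety Monitoring Plan: after weighing risks and benefits, the board issues a "recommendation as to whether the study should continue, whether modification to the study are needed or if the study should be terminated".

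Under section 2 the board is advisory. The sponsor-investigator decides whether the trial continues, and a memo must justify any departure from a board recommendation.

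**The concern.** Section 7 reaches safety by its own words. An excess of seizures in an active arm is evidence that sham has the better side-effects profile, which is the situation the sentence describes. The sentence then says the study continues unless half of the variables differ significantly. A serious harm will often show in one event type only. Seizure is the obvious case here: the protocol's background section on rTMS safety discusses it, and the exclusion criteria name it as a contraindication to the stimulation.

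If such a signal appeared, the board would hold two instructions pointing different ways: the SAE review and safety duty would let it recommend stopping, while its only statistical guideline would tell it to continue. The sponsor-investigator could cite section 7 in the memo that section 2 requires when a board recommendation is not followed. The point concerns safety stopping only. It does not concern the error rate of an early stop for efficacy.

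**Working it through.** The 50% threshold is a bare rule with no inputs behind it, so there is no figure of the plan's to reproduce. The check has three parts.

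**1. Provisions side by side.**

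| Provision | Covers safety? | Significance needed? | Says which prevails? |
|---|---|---|---|
| Manual, section 7 | Yes, side effects named | Yes, in at least 50% of variables | No |
| Manual, section 2 (safety duty) | Yes | No | No |
| Manual, section 4 (SAE review) | Yes | No | No |
| Data Safety Monitoring Plan (risk-benefit report) | Yes | No | No |

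The one explicit safety override in the documents is in the Data Safety Monitoring Plan: "The study blind may be broken at any point throughout the study as needed to protect the safety of a subject". It concerns an individual's treatment code, not termination of the study.

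**2. Can one variable meet the condition?** With *m* variables, the number that must be significant is ceil(*m*/2), and one variable is a share of 1/*m*.

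| *m* | Needed | Share from one variable | Met by one variable? |
|---|---|---|---|
| 1 | 1 | 100% | Yes |
| 2 | 1 | 50% | Yes |
| 3 | 2 | 33% | No |
| 11 | 6 | 9% | No |

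The row *m* = 11 assumes the variables are the 10 procedures in the aphasia testing table (Day 2) plus one safety variable. For any *m* of 3 or more, the size of the difference is irrelevant: 15 of 15 against 0 of 15 gives p = 1.3 × 10⁻⁸ and still fails.

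**3. What would significance on one safety variable take?** This is an illustration of the second hurdle inside the same condition. From the documents: 15 subjects per group in four groups (Aim 1). Assumed: two-sided Fisher exact test, no events in sham, alpha as shown, and a look at half enrolment with 8 per arm. For equal arms of size *n*, with *k* events all in the active arm, p = 2 × C(*n*,*k*) / C(2*n*,*k*).

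- 15 against 15, *k* = 4: 2 × 1,365 / 27,405 = 0.0996.
- 15 against 15, *k* = 5: 2 × 3,003 / 142,506 = 0.042.
- 15 against 15, *k* = 7: 2 × 6,435 / 2,035,800 = 0.006.
- 8 against 8, *k* = 4: 2 × 70 / 1,820 = 0.077.
- 8 against 8, *k* = 5: 2 × 56 / 4,368 = 0.026.

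At 15 per arm the smallest qualifying counts are therefore 4, 5 and 7 of 15 at alpha 0.10, 0.05 and 0.01 (6 of 15 gives 0.017). At alpha 0.05, 4 of 15 (27%) does not qualify. At half enrolment, 5 of 8 (63%) is needed.

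For the three active arms pooled against sham, the Fisher test gives:

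- 45 against 15: 11 events, p = 0.051; 12 events, p = 0.027.
- 24 against 8: 9 events, p = 0.070; 10 events, p = 0.035.

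**The case against.** The best defence is that section 7 concerns comparative findings between arms, while SAEs have their own clause in section 4, and the specific clause should govern. On that reading only a cross-reference is missing. A serious seizure would reach the IRB, the DSMB and the funder's project officer within 72 hours, and ad hoc meetings are allowed. Subjects who no longer meet the eligibility criteria are withdrawn. The DSMB report goes to the IRBs and the funder. Any memo rejecting the board's advice accompanies minutes that the IRB receives. So the trial has real safety protection outside section 7, and misuse of the section would be visible.

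All of that stands, and it rules out any claim that the trial cannot be stopped for harm. It does not settle the conflict. The narrower reading is reasonable, but the text does not state it. SAEs are a kind of adverse event, and a side-effects profile does not naturally exclude them. Withdrawing one subject is also not a decision about the study.

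Two objections to the numbers are fair. The 6-of-11 figure rests on an assumed list. If side-effect variables were counted separately and there were only one or two, a single significant difference would satisfy the condition. The Fisher counts depend on an assumed test, alpha and sham rate; they illustrate the height of the bar and are not needed for the main argument.

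**Conclusion.** The concern holds. Section 7 applies the 50% condition to side effects and has no safety exception. Nothing in the documents makes it give way to the SAE review, the safety duty or the risk-benefit recommendation. That conclusion rests on the text alone.

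The claim that a single-variable harm cannot meet the condition needs only that three or more variables are counted together. The consequence is a written reason to continue in the face of a concentrated harm. It is not a prediction that the SAE route would be ignored. Given the other routes, this is something the sponsor should fix, not a fatal flaw.

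**What to change.** In section 7, delete the reference to the side-effects profile so that the condition covers better efficacy only. Then add:

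> This condition does not apply to safety. A DSMB recommendation to pause, modify or terminate for safety rests on its risk-benefit judgement of AEs and SAEs, may rest on a single serious event type, needs no statistically significant difference, and prevails over this section.

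This follows the direction of section 4 and the Data Safety Monitoring Plan, but the wording on pausing, a single event type, the absence of a significance requirement and precedence is new and needs the sponsor's agreement. A lighter alternative is one sentence saying that section 7 does not limit recommendations made on safety grounds. That would remove the conflict while leaving a significance rule for minor tolerability differences.

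The cost is one deletion and two sentences in the charter, with no change to sample size or analysis. The downside is that the board could recommend action on a small imbalance that arose by chance. That risk is modest, since the board includes a statistician and its recommendations are advisory.
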